5.5 Study Completion and Discontinuation Criteria

5.5.1 Study Completion/Withdrawal

A subject will have the right to withdraw from the study at any time for any reason.

A subject will be discontinued from the study by the Investigator if unacceptable toxicity or withdrawal of consent occurs.

Subjects participating in a MAD cohort that is determined to be greater than the MTD based on dose escalation rules can opt to continue in the study at the next lower dose cohort (ie, at the MTD).

Subjects withdrawn from SAD cohorts should have all assessments conducted at the End of Study Visit at the time of withdrawal. Subjects withdrawn from MAD cohorts should have all

assessments conducted at the End of Treatment Visit as well as the End of Study Visit, for safety monitoring purposes.

Subjects who have completed a SAD cohort are eligible to participate in a MAD cohort, provided there is at least 90 days between the dose in the SAD cohort and the first dose in the MAD cohort.

Allergic reactions may include local dermatitis, angioedema, throat constriction, or anaphylaxis. Appropriate treatment may include administration of antihistamines, hydrocortisone, or epinephrine at the discretion of the assessing physician. Subjects diagnosed with a systemic allergic reaction requiring therapy will be withdrawn from the study.

Given the proposed mechanism of action of QR-010, it could be anticipated that subjects could experience a change in baseline cough, change in sputum quality, or change in sputum volume. A pulmonary exacerbation should be considered if these symptoms are accompanied by fever, body weight loss, generalized malaise. If a pulmonary exacerbation is diagnosed, appropriate interventions including appropriate additional antibiotics should be prescribed by the Investigator or treating physician. Subjects diagnosed with a pulmonary exacerbation requiring the addition of antibiotics will be withdrawn from the study.

5.5.2 Criteria for Study Drug Discontinuation

Subjects should be continued on study treatment unless an intolerable AE is experienced, or until an SAE and/or Grade ≥ 2 AE in the same system organ class is experienced by two or more subjects in the same cohort. Study treatment for that dose cohort should be stopped and subjects advised regarding available treatment options.

When study treatment is discontinued in the MAD cohorts due to an intolerable AE, the Investigator should obtain all procedures specified for the End of Treatment Visit, followed by an End of Study Visit, conducted 28 days after the last study drug dose.

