The AEs of Interest listed in Table 2 are AEs commonly seen with inhaled products. If AEs of interest occur at a Grade 2 level or higher in a single subject in a cohort, then an additional 4 subjects will be added to the cohort. Any of the Grade ≥ 2 toxicities shown in Table 2, as well as

any other respiratory AEs reported, will be evaluated and considered when making dose escalation decisions. If no additional subjects experience any Grade ≥ 2 AEs of Interest, dose escalation may proceed (if recommended by the DSMC).

The Investigator will base decisions to de-escalate to a lower dose, hold the dose (delay or skip), or discontinue study drug for an individual subject using the CTCAE (modified for CF) toxicity grades, in consultation and agreement with the Sponsor’s Medical Monitor. In addition to the CTCAE (modified for CF) toxicity grades, the Investigator should also review the stopping rules in Section 5.5.3 with regard to decreases in FEV₁.

For the multiple dose cohorts, subjects who experience a DLT (defined in Section 4.4) should be discontinued from study drug (whether or not the event resolves), and the End of Treatment Visit procedures should be conducted. An End of Study Visit should also be conducted 28 days after the last study drug dose.

Table 2: Adverse Events of Interest

| Adverse Event of Interest | Symptoms (Grade ≥ 2 per CTCAE or as Specified Below) |
|--------------------------------------|------------------------------------------------------------------------------------------------------------------------------------------|
| Atelectasis | Symptomatic (eg, dyspnea, cough); medical intervention indicated (eg, chest physiotherapy, suctioning); bronchoscopic suctioning |
| Hypotension | non-urgent medical intervention indicated |
| Bronchospasm | symptomatic, medical intervention indicated |
| Liver Function Test Elevation | alanine aminotransferase (ALT) > 3-5 x ULN or aspartate aminotransferase (AST) > 3-5 x ULN AND a doubling from the baseline value |
| Pneumonitis | Symptomatic; medical intervention indicated; limiting instrumental ADL |
| Crackles | Scattered or focal |
| Dyspnoea | Shortness of breath with minimal exertion; limiting instrumental ADL |
| Hypoxia | Decreased oxygen saturation with exercise (eg, pulse oximeter < 88%); intermittent supplemental oxygen |

ADL = Activities of Daily Living

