5.5.3.2 Stopping Rules for Individual Subjects

For individual subjects in the SAD cohorts, any of the criteria below will result in discontinuation of study drug administration in the SAD portion of the study, as well as exclusion from participation in the MAD portion. These subjects will continue to be followed for safety through the End of Study visit.

- Any SAE suspected of being related to study drug
- Any Grade ≥ 2 AE suspected of being related to study drug
- Decrease in absolute FEV₁ volume of $\geq 15\%$ from baseline value following study drug administration
- Unacceptable toxicity considered by the Investigator to be related to study drug treatment
- Further treatment is deemed to be unsafe in the Investigator's clinical judgment. The decision to discontinue a subject may also result from any clinically significant alteration in any clinical or laboratory finding
- If at any time the subject fails to follow the requirements of the protocol
- The subject withdraws consent. Subjects may withdraw from the study at any time without repercussion to their treatment or affiliation with their healthcare providers.

For individual subjects in the MAD cohorts, any of the following will result in permanent discontinuation of study drug:

- Any SAE suspected of being related to study drug
- Any Grade ≥ 2 AE suspected of being related to study drug
- Cumulative decrease in absolute FEV₁ volume of $\geq 15\%$ from baseline value following study drug administration
- Unacceptable toxicity considered by the Investigator to be related to study drug treatment
- Further treatment is deemed to be unsafe in the Investigator's clinical judgment. The decision to discontinue a subject may also result from any clinically significant alteration in any clinical or laboratory finding
- If at any time the subject fails to follow the requirements of the protocol
- The subject withdraws consent. Subjects may withdraw from the study at any time without repercussion to their treatment or affiliation with their healthcare providers.

If study drug is discontinued for any of these stopping rules, administration will not be resumed, even after resolution of the event.

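### Section 5.5.2, read literally, keeps a MAD subject on study drug after a tolerable, suspected-related Grade ≥2 AE, although Section 5.5.3.2 requires a permanent stop; precedence is not stated

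*Protocol*

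**What the plan says.** Four parts of the protocol bear on whether one MAD subject stays on drug after an adverse event.

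- **5.5.2 (Criteria for Study Drug Discontinuation)** sets continuation as the default: "Subjects should be continued on study treatment unless an intolerable AE is experienced", or until a serious or Grade ≥2 event in one system organ class "is experienced by two or more subjects in the same cohort". In the second case treatment stops for the whole dose cohort. The section does not mention relatedness, does not define intolerable and does not refer to 5.5.3.2.
- **5.5.3.2 (Stopping Rules for Individual Subjects)** is mandatory: "For individual subjects in the MAD cohorts, any of the following will result in permanent discontinuation of study drug". The list includes any Grade ≥2 AE suspected of being related. It closes: "If study drug is discontinued for any of these stopping rules, administration will not be resumed, even after resolution of the event".
- **4.3 (Dose Escalation)** covers "decisions to de-escalate to a lower dose, hold the dose (delay or skip"), with stopping as a third option. The choice for each subject rests on the modified CTCAE grade and needs the Medical Monitor's agreement. It adds that the Investigator "should also review the stopping rules in Section 5.5.3 with regard to decreases in" FEV1. Its next paragraph says that MAD subjects with a DLT "should be discontinued from study drug (whether or not the event resolves").
- **6.4 (Adverse Reaction Management)** repeats that a Grade ≥2 reaction suspected of being related leads to discontinuation.

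SAP 2.5.1 describes subject-level stopping only as the subject's choice or the Investigator's medical judgment, and does not settle the matter.

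**The concern.** A site that opens the section titled as the criteria for discontinuing study drug finds an instruction to continue, with its own exceptions. A single tolerable Grade ≥2 event meets neither exception, even if it is thought to be drug-related. A few lines later, the individual stopping rule takes the same subject off drug for good.

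The case is foreseeable. Where the CTCAE listing has no criteria for an event, Table 4 in 12.3.1 makes Grade 2 an event that needs minimal or noninvasive treatment or interferes with daily activities, and many such events are tolerable. Under 12.3.2 the temporal link for a related event need only be possible, provided that nothing else readily explains the event.

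Section 13.1 describes this as a first-in-human trial. What is at stake is further dosing of a subject whom the protocol's own rule would stop, and different handling of the same event across roughly 20 (5.2) to 27 (synopsis) sites. Continuing under 5.5.2 involves no Medical Monitor step.

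**Working it through.** **Test case.** One MAD subject has an event after dose k of 12. It is Grade 2 or higher, tolerable, suspected of being related, and not a DLT. No other subject in the cohort has had a serious or Grade ≥2 event in that organ class.

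| Section | Force | Applied to this subject |
|---|---|---|
| 5.5.2 | should | Continue: neither exception is met |
| 5.5.3.2 | will | Stop permanently; no resumption |
| 6.4 | will | Stop |
| 4.3 | permits | Hold, lower the dose or discontinue, with Medical Monitor agreement |

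**Does tolerability reconcile 5.5.2 with 5.5.3.2?** No. The related Grade ≥2 criterion carries no tolerability condition, and unacceptable toxicity is a separate item in the same list. The Grade ≥2 item is therefore meant to apply without it.

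**Does the 4.3 cross-reference bring in the rule?** Not for this event. It is limited to FEV1 decreases.

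**Further doses at issue.** Inputs: 12 MAD doses (synopsis; 4.2), and missed doses are not made up (7.1).

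- 5.5.3.2: 0 further doses for any k.
- Literal 5.5.2: up to 12 − k. For k = 1, 12 − 1 = 11; for k = 4, 12 − 4 = 8; for k = 11, 12 − 11 = 1.
- A 4.3 hold of h doses: up to 12 − k − h. For k = 1 and h = 1, 12 − 1 − 1 = 10.

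**Subjects in scope.** Planned MAD enrolment is 4 × 8 = 32, of whom 4 × 6 = 24 receive QR-010. SAD subjects receive one dose, so no later dose is at issue.

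**Limit of the conflict.** Once a second subject in the cohort has a serious or Grade ≥2 event in the same organ class, 5.5.2 itself stops the cohort. The contradiction therefore covers the first affected subject per organ class in each cohort. The documents give no event rate, so no frequency can be estimated.

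**The case against.** The strongest reply is that the protocol already answers the question, twice and in mandatory terms. 5.5.3.2 is the specific rule for individual subjects, 6.4 repeats it, and 5.5.2 is a general recommendation placed just before it. Nor can 5.5.2 be a closed list. Read that way, it would also continue subjects after withdrawal of consent, a tolerable FEV1 fall of 15% or more, a tolerable DLT, or an exacerbation needing added antibiotics (5.5.1). This stands as evidence of intent, and it lowers the severity. It does not supply the missing precedence: 5.5.2 is still worded as an instruction to continue and has no pointer to the rule that overrides it.

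Other safeguards also narrow the exposure. DLT subjects come off drug under 4.3 whether or not the event resolves, and under SAP 2.5.2 Grade ≥2 AEs of interest go to the DSMC without waiting for the cohort to finish. Neither reaches a related Grade ≥2 event that is not an AE of interest or a DLT.

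A reader might infer three stronger points that the documents do not support.

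- *That 4.3 tells sites to keep dosing.* It offers options, discontinuation among them, and requires Medical Monitor agreement. Its fault is only that it does not exclude events meeting a stopping rule.
- *That 6.4 opens a route to restart.* It allows re-initiation after a Grade 2–3 toxicity during administration that resolves promptly, but the next sentence stops suspected-related Grade ≥2 reactions.
- *That lost data are a cost of the contradiction.* The absence of Dose 12 PK parameters after early discontinuation (SAP 3.1.2), and exclusion from the post hoc Per Protocol population for fewer than 10 doses, both follow from applying 5.5.3.2 as written.

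**Conclusion.** Wrong as written: a safety stopping rule is contradicted by a neighbouring section, at low-to-moderate severity. For the first MAD subject in a cohort with a tolerable, suspected-related, non-DLT Grade ≥2 event in a given organ class, 5.5.2 read literally allows up to 12 − k further doses (at most 11), and 5.5.3.2 allows none. The dose counts are upper bounds. They assume that a site follows 5.5.2 literally despite two mandatory provisions to the contrary, and that no later event stops the subject or the cohort. The conclusion also assumes that not every related Grade ≥2 event counts as intolerable; if it did, the two sections would agree, but nothing in the documents says so.

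**What to change.** 1. **5.5.2:** begin the continuation sentence with *Subject to the individual stopping rules in Section 5.5.3.2*.
2. **4.3:** widen the cross-reference from FEV1 decreases to the full 5.5.3.2 list, and state that a hold or a lower dose applies only where no 5.5.3.2 criterion is met.

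Section 6.4 should stay as it is. Limiting its restart sentence further would add a real-time causality and DLT judgment during nebulization, which is new procedure. A DLT exclusion in 4.3 is also unnecessary, because that section already discontinues DLT subjects.

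The cost is two wording edits, with the approvals that 14.1 requires for any amendment. Sample size, visits and procedures do not change. Subjects whom a literal reading of 5.5.2, or a hold under 4.3, would have kept on drug will be stopped, with some loss of later on-treatment data and Dose 12 PK parameters. Relative to 5.5.3.2 as it stands, nothing further is lost.

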5.5.3 Stopping Rules

5.5.3.1 Stopping Rules for Study

The DSMC will evaluate the safety data after each dose cohort and thereafter on an ongoing basis to recommend if the study should continue or cease, or if any modifications should be made as to how subjects are treated or managed.

5.5.3.2 Stopping Rules for Individual Subjects

For individual subjects in the SAD cohorts, any of the criteria below will result in discontinuation of study drug administration in the SAD portion of the study, as well as exclusion from participation in the MAD portion. These subjects will continue to be followed for safety through the End of Study visit.

- Any SAE suspected of being related to study drug
- Any Grade ≥ 2 AE suspected of being related to study drug
- Decrease in absolute FEV₁ volume of $\geq 15\%$ from baseline value following study drug administration
- Unacceptable toxicity considered by the Investigator to be related to study drug treatment
- Further treatment is deemed to be unsafe in the Investigator's clinical judgment. The decision to discontinue a subject may also result from any clinically significant alteration in any clinical or laboratory finding
- If at any time the subject fails to follow the requirements of the protocol
- The subject withdraws consent. Subjects may withdraw from the study at any time without repercussion to their treatment or affiliation with their healthcare providers.

For individual subjects in the MAD cohorts, any of the following will result in permanent discontinuation of study drug:

- Any SAE suspected of being related to study drug
- Any Grade ≥ 2 AE suspected of being related to study drug
- Cumulative decrease in absolute FEV₁ volume of $\geq 15\%$ from baseline value following study drug administration
- Unacceptable toxicity considered by the Investigator to be related to study drug treatment
- Further treatment is deemed to be unsafe in the Investigator's clinical judgment. The decision to discontinue a subject may also result from any clinically significant alteration in any clinical or laboratory finding
- If at any time the subject fails to follow the requirements of the protocol
- The subject withdraws consent. Subjects may withdraw from the study at any time without repercussion to their treatment or affiliation with their healthcare providers.

If study drug is discontinued for any of these stopping rules, administration will not be resumed, even after resolution of the event.

6.0 INVESTIGATIONAL PRODUCT(S)/STUDY MEDICATIONS

6.1 Investigational Product

6.1.1 QR-010

The investigational drug product, QR-010 Solution for Nebulization, is available at a concentration of 50 mg/mL (2 mL/vial) in a sterile isotonic solution of sodium chloride in water for injection. QR-010 Solution for Nebulization is a clear, colorless solution. The pH is between 6 and 8, and QR-010 Solution for Nebulization storage condition is 2-8°C. QR-010 Solution for

Nebulization will be administered to the subjects via oral inhalation, using the designated nebulizer.

6.1.2 Diluent and Placebo

Placebo Solution for Nebulization will be the same as the diluent for QR-010 Solution for Nebulization. It is 10 mL 0.9% isotonic solution of sodium chloride in water for injection. It is a clear, colorless solution. Placebo Solution for Nebulization will be administered to the subjects via inhalation, using the nebulizer described in Section 6.2.

6.1.3 Packaging and Labeling

QR-010 Solution for Nebulization is supplied in 2 mL Type 1 glass vials with a grey bromobutyl rubber stopper and a light blue tear off seal. Vials are packed into an outer carton, which is labeled per country-specific requirements.

Placebo Solution for Nebulization is packaged in 10 mL individual, sterile plastic vial/ampules.

Each vial/ampule and carton is labelled to comply with local guidelines.

6.1.4 Drug Shipment and Storage

An initial supply of QR-010 Solution for Nebulization will be shipped refrigerated (2-8°C) to the site investigational pharmacy upon completion of site activation process. Re-supply will occur through the central inventory management system. The drug should be stored refrigerated in the site pharmacy or a designated locked area at 2-8°C until use.

Please refer to the Study Manual for additional details on site activation, drug supply and the central inventory management system.

6.1.5 Drug Accountability and Reconciliation

The Investigator must designate a research pharmacist or other staff member to be unblinded and maintain an inventory record of drugs received and dispensed. Used vials should be retained for drug accountability by the site monitor, unless prohibited by local procedures, in which case an alternative drug accountability process will be agreed upon with the Sponsor. It is acceptable to destroy used vials per site standard operating procedure (SOP) after drug accountability has been completed by the site monitor. Additional details on study drug handling will be provided in the Pharmacy Manual.

Forms will be provided to facilitate the inventory control. These forms must be used unless the Investigator has previously established a system that complies with local regulations and is approved by Sponsor. The study drug must be dispensed only at the institution(s) specified on form FDA 1572 or Statement of Investigator (as applicable).

Upon completion or termination of the study and after inventory by a Sponsor-designated monitor, it will be determined if unopened drug is to be sent to the Sponsor in the original containers or is to be destroyed on site. Residual solutions must be discarded after use.

6.1.6 Dosage and Administration

The pharmacist (or other personnel qualified to prepare study drug for administration) at each site will receive study drug and will prepare and/or dilute the study drug according to the Pharmacy Manual for each administration. Pharmacy staff will be unblinded to subject treatment assignment (as assigned by the designated randomization system for the study). All other study site staff, including the Investigator and subjects, will be blinded to study treatment assignment.

Study drug doses will only be administered by a healthcare professional in an in-clinic setting. No at-home dose administration will be allowed. Subjects will receive study drug by inhalation via nebulizer. No other medications should be mixed with study drug in the nebulizer medication chamber. Appropriate study drug dilutions or placebo will be prepared by an Unblinded Study Pharmacist, as detailed in the Pharmacy Manual. The prepared doses will be loaded into the nebulizer medication chamber by study staff just prior to administration to the subject.

6.1.7 Overdose

The effects of overdose of this product are not known.

6.1.8 Premedication

For subjects whose standard CF medications include a short-acting β -agonist (SABA), the SABA should be administered within 15 minutes to 2 hours prior to the first study drug dose. If no adverse reaction occurs with the first dose, subsequent doses need not be preceded by a SABA, as determined by the Investigator.

For those subjects whose standard CF medications include a long-acting β -agonist (LABA), the LABA should be administered between 1 and 4 hours prior to each study drug dose.

6.2 Nebulizer

6.2.1 eFlow Nebulizer System

The eFlow® Nebulizer System [REDACTED] will be used for study drug administration in the EU. The Investigational eFlow® Nebulizer System [REDACTED] will be used for study drug administration in North America.

Study drug dose dilutions prepared by the unblinded pharmacist will be provided to the study staff (who are blinded to the treatment assignment) who will load the medication chamber of the eFlow nebulizer with the study drug dose specified by randomization. The nebulizer Instructions for Use will be followed for all subjects for study drug administration. To minimize cross contamination between subjects, a new nebulizer handset will be provided for each dose.

Study drug will be administered in the clinic by qualified site personnel via the designated study nebulizer, until all study drug solution has been administered. Complete administration of study drug/placebo, if uninterrupted, should take approximately less than 20 minutes (a minimal amount of study drug solution will remain in the nebulizer medication chamber—this is normal).

6.3 Concomitant Medications and Ancillary Therapy

6.3.1 Permitted Concomitant Medications

All concurrent CF therapies should be continued for the duration of the study. Prior to study drug dosing on a given day, the following order of concurrent treatment should be adhered to: Long- and/or Short acting bronchodilator, mucolytic therapy (eg, Pulmozyme), chest physiotherapy (airway clearance technique), inhaled corticosteroid, inhaled antibiotics.

Subjects who are prescribed chronic, intermittent inhaled antibiotics should participate in the study when they are most stable and continue the inhaled antibiotic throughout the study. For most patients, this would mean that the subject initiates the inhaled antibiotic during the screening period and continues taking it as prescribed through the end of study, including some additional days or weeks. As the regimens of chronic inhaled antibiotics varies significantly from patients to patient, the Investigator is encouraged to discuss with the Sponsor's Medical Monitor the appropriate regimen for the course of the study.

Ancillary therapy regimens and airway clearance techniques should remain consistent throughout the study period. Other ancillary therapy may be administered at the discretion of the Investigator. Subjects should receive full supportive care, including antibiotics, antiemetics, bronchodilators, etc., as appropriate. The reason(s) for ancillary therapy, including dosage and date(s) of treatment, will be recorded in the source documents.

